#### 4.2.1 Eligibility for Ongoing Immune Function Screening

If the  $\text{TNF}$  response is  $> 200$  pg/ml and the ferritin level is  $< 2,000$  ng/ml on the initial screening sample, the subject will undergo repeat immune function screening according

to the schedule described in section 4.2 above, unless any of the following occur:

Immune function screening will be temporarily paused in the event of the following:

- WBC count  $< 2K$  on the planned screening day
- Initiation of CRRT or ECMO
- Immune function screening will resume on the next planned sampling day once the WBC count is  $\geq 2K$  or the subject comes off CRRT or ECMO provided that the subject remains in the ICU, still has MODS, and has no other exclusions.

Immune function screening will be permanently discontinued in the event of the following:

- Documentation (either through study-specific or clinical laboratory findings) of serum ferritin level  $\geq 2,000$  ng/ml
- Confirmation of a diagnosis other than sepsis
- Diagnosis of pregnancy
- Initiation of new major immunosuppressive therapy (See Manual of Operations for list)

### 4.3 Eligibility to Receive Initial GM-CSF Dose

Subjects eligible to be considered for initial administration of GM-CSF will receive study drug if the following additional requirements are met:

- No diagnosis of pregnancy.
- The presence of dysfunction of at least one organ system
- Subject remains in ICU.
- WBC  $\leq 50K$  cells/mm^3.
- CRRT is not being used and there are no immediate plans to start.
- No new immunosuppressive drugs are being given or planned in the next 7 days.
- Not on ECMO or have immediate plans to start ECMO.

The WBC measurement is required prior to GM-CSF, and must be the most recent measurement prior to drug administration. The sample must be no earlier than 6 hours prior to drug administration.

## 4.4 Eligibility to Receive Subsequent GM-CSF Doses

Subjects will continue to receive GM-CSF for up to 7 days but must continually qualify by meeting the following criteria:

- Not pregnant (pregnancy is a permanent disqualification for drug; stop screening)
- Subject remains in hospital (ICU not required).
- $WBC \leq 50K$  cells/mm^3.
- Absence of documentation (through clinical laboratory findings) of serum ferritin level  $\geq 2,000$  ng/ml.

The WBC measurement is required prior to GM-CSF, and must be the most recent measurement prior to drug administration. The sample must be no earlier than 6 hours prior to drug administration. If the WBC exceeds 50K cells/mm^3, GM-CSF should be withheld on this study day. The subject may be re-assessed for GM-CSF on the next day (up to Drug Day 7).

Repeat sampling for testing innate immune function and ferritin levels is conducted on Drug Day 4. On Drug Day 5, GM-CSF should not be administered until verification that the ferritin remains below 2,000 ng/ml. If the ferritin measurement from Drug Day 4 indicates hyperferritinemia ( $\geq 2,000$  ng/ml), all subsequent study drug administration will stop, and the site will be immediately notified so that the hyperferritinemia can be confirmed and managed according to site clinical protocols.

On each day, it must be verified that if there have been serious adverse events that are related or probably related to GM-CSF, the treating physician authorizes the safety of continued GM-CSF administration.

## 4.5 Assignment of Treatment Arms

Study drug will be administered in 4 sequential treatment arms (125 mcg/m^2/day IV, 250 mcg/m^2/day IV, 125 mcg/m^2/day SQ, 250 mcg/m^2/day SQ) dependent on the success of an arm. Enrollment will begin in the 125 mcg IV arm. If 125 mcg IV does not prove successful, we will move to the 250 mcg IV dose arm. If an IV arm is successful, we will open a SQ arm at the same treatment dose level that the IV arm completed. If we begin with 125 mcg SQ arm, then we will move to the 250 SQ arm if the 125 SQ arm is not successful.

A subject is considered to have failed to achieve resolution of immunoparalysis if the  $\text{TNF}\alpha$  response is  $< 200$  pg/ml on Drug Days 4 or 8. If a 3rd subject in a 125 mcg dose arm fails to respond to study drug, that arm is considered to have failed, and no further subjects will be enrolled in that arm. Enrollment will proceed to the 250 mcg arm for the respective route (IV or SC). In the 250 mcg arms, we will enroll fully to ten evaluable subjects even if these arms have 3 or more subjects who do not respond. This is to fully understand the PK of the drug at this FDA approved dose.

A successful dose and route is defined as the resolution of immunoparalysis in 8 out of the first 10 subjects in a treatment arm. Enrollment will not stop early in a study treatment arm due to achieving 8 successes. Instead we will continue to enroll until that study treatment arm is complete and we have confirmed that the arm has a sufficient number (ten) of evaluable subjects who have received study drug.

## 4.6 Achieving Enrollment Balance

Corticosteroid use and subject age represent potentially important variables to consider since it is not clear how they will impact the effect of GM-CSF on immune function. We will make good-faith efforts to enroll some subjects with and without corticosteroid use, and we will make good-faith efforts to achieve a similar distribution of ages in our final IV and SQ arms. The study investigator may choose not to approach the legal guardian(s) of otherwise eligible patients if the age or steroid bins (defined below) for that subject are already filled. However, it is left to the discretion of the study investigator to override these requirements if they cause undue delays in enrollment.

**Corticosteroid use.** Corticosteroid use will be assessed at the time of assessment for enrollment eligibility and subjects will be classified by whether or not they are using corticosteroids at that time. For each treatment arm, we will enroll to allow for a 60%/40%, 50%/50%, or 40%/60% split of corticosteroid exposure at time of screening. If the bin to which a screened subject belongs (using corticosteroids vs. not using corticosteroids) already has six evaluable subjects, then the bin is closed and the subject will not be enrolled in the study. When a new dose/route arm is initiated the bins are reset to zero.

**Age.** Subjects in the IV treatment arm(s) will be recruited without regard to age (other than that stipulated in the eligibility criteria). However, in order to ensure that subjects in the final SQ arm have a similar age distribution to the final IV arm, subjects will enroll into one of two age bins. The first bin will be for subjects no older than the median age

from the final IV arm. The second age bin will be for older subjects. We will require a 60%/40%, 50%/50%, or 40%/60% split between the two age bins analogously to the corticosteroid use bins.

## 4.7 Subject Replacement

In the event that a subject newly develops an exclusion criterion after GM-CSF treatment has begun, i.e. the discovery of an allergy to GM-CSF, the following approach to drug delivery and replacement in the study treatment arm will be taken:

- **Ferritin  $\geq 2,000$  ng/ml:** If a subject develops a serum ferritin level  $\geq 2,000$  ng/ml as measured on the post-3rd dose sample, GM-CSF will be discontinued and the study team will be notified so that they may confirm the ferritin level at their institution per the treating team. This subject **will be replaced** in the study treatment arm.
- **Initiation of CRRT or ECMO:** The initiation of CRRT or ECMO may affect the PK/PD of GM-CSF. If a subject is newly placed on CRRT or ECMO while receiving GM-CSF, GM-CSF treatment will continue and PK and immune function testing will continue per protocol, however the subject's data will not be used for determination of treatment success. This subject **will be replaced** in the study treatment arm.
- **Serious AE:** If a subject's GM-CSF is discontinued as the result of an SAE that is perceived to be drug-related, the subject **will be replaced** in the study treatment arm.
- **Pregnancy:** If pregnancy is diagnosed in a subject who is receiving GM-CSF, the study drug will be stopped and the subject **will be replaced** in the study treatment arm.
- **Drug interruption:** If a subject who is assigned to study drug does not receive all 7 doses of GM-CSF (except for WBC  $> 50,000$ ), the subject **will be replaced** in the study treatment arm.
- **Initiation of major immunosuppressive therapy:** If a subject who is receiving GM-CSF is prescribed new immunosuppressive therapy (See Manual of Operations for list) study participation will be concluded and the subject **will be replaced** in the study treatment arm. GM-CSF therapy can continue at the discretion of the clinical team. If GM-CSF is **continued**, Day 4 and Day 8 samples should still be collected.

- **WBC > 50,000:** If one or more doses of GM-CSF are held due to a subject's WBC count being  $> 50,000$  cell/mm^3, sampling will continue on what would otherwise have been the morning after the 3rd and 7th scheduled doses. Samples will be collected and data will be analyzed per protocol and the subject **will be included** in the study treatment arm.
- **Confirmed diagnosis other than sepsis:** If a subject is later determined definitively to have a diagnosis other than sepsis that lead to sepsis-like symptoms, this subject **will be replaced** in the study treatment arm.
- **Missing/unusable immune function sample:** On Drug Day 4 or Drug Day 8 immune function testing samples are collected for a subject. If a subject's sample from either of these days was not obtained or was obtained but found to be unusable, this subject **will be replaced** in the study treatment arm.
- **Hospital Discharge:** If a subject who is receiving GM-CSF is discharged from the hospital prior to receiving all doses, this subject **will be replaced** in the study treatment arm.
- **Study Withdrawal:** If a subject who is receiving GM-CSF is withdrawn from the study, this subject **will be replaced** in the study treatment arm.

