## 3 Subject Eligibility, Accrual and Study Duration

### 3.1 Eligibility criteria

Inclusion criteria are:

- $\geq 40$  weeks gestational age to  $< 18$  years; AND
- Onset of  $\geq 2$  new organ dysfunctions (compared to pre-sepsis baseline) as measured by the Proulx criteria; AND
- Documented or suspected infection as the MODS inciting event.

Exclusion criteria are:

- Weight  $< 5\text{kg}$ ; OR
- Limitation of care order at the time of screening; OR
- Patients at high risk for brain death; OR
- Active (or planned within 7 days) immunosuppressive treatment; OR
- Known primary immunodeficiency disorder; OR
- Diagnosis of myeloid leukemia, myelodysplasia, or autoimmune thrombocytopenia; OR
- Known allergy to GM-CSF; OR
- Documented hyperferritinemia (serum ferritin  $\geq 2,000$  ng/ml) during current sepsis event; OR
- Contraindication to SQ injection (ECMO); OR
- Burns where  $> 5\%$  of the total body surface area is affected; OR
- Renal replacement therapy at the time of screening; OR
- On ECMO or anticipated to require ECMO; OR
- Known pregnancy; OR
- Inability to collect and ship sample for immune testing on MODS Day 2; OR
- Previous enrollment in the GRACE study.

These criteria were chosen in order to identify children with early, sepsis-induced MODS and to exclude children for whom GM-CSF is unlikely to be beneficial (children with limitation of care orders), those for whom the effect of GM-CSF may be altered by the receipt of active immunosuppression, those with known contraindications to GM-CSF, and those with concurrent secondary hemophagocytic lymphohistiocytosis (HLH) or macrophage activation syndrome (MAS).

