### 3.2 Subject Accrual and Study Duration

This study will require 20 to 30 evaluable subjects. We define an evaluable subject as a subject who receives all 7 doses of GM-CSF (with an exception made when WBC > 50K cells/mm^3), and from whom both Drug Day 4 and Drug Day 8 immune testing samples were obtained. We anticipate that approximately one third of enrolled subjects will qualify to receive GM-CSF, and anticipate that half of the subjects receiving GM-CSF will be evaluable due to post-enrollment exclusions described below. This will require enrollment of up to 180 subjects.

The CPCCRN network enrolled over 400 subjects with multiple organ failure in two years in a previous study. We estimate that each of the eight participating hospitals will have 8 to 10 eligible patients per year. Study completion will require up to three years of subject accrual.

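### Section 4.7 keeps GM-CSF going in a child newly placed on ECMO, with no exception for the SQ arms, although section 3.1 treats ECMO as a contraindication to SQ injection

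*Combined protocol and SAP*

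**What the plan says.** Section 4.7 sets out drug delivery and replacement for a subject who meets an exclusion criterion after dosing has started. For CRRT or ECMO it reads: "If a subject is newly placed on CRRT or ECMO while receiving GM-CSF, GM-CSF treatment will continue". PK and immune testing also go on, the child's data are not used to judge treatment success, and the child is replaced. The only reason given is a possible effect on the drug's PK/PD.

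Section 3.1 excludes ECMO twice. One bullet begins "Contraindication to SQ injection (ECMO"; the other reads "On ECMO or anticipated to require ECMO". The first gives a reason tied to the route of injection. The second applies whatever the route.

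Section 4.3 allows the first dose only if the child is "Not on ECMO or have immediate plans to start ECMO". For later doses, section 4.4 says: "Subjects will continue to receive GM-CSF for up to 7 days but must continually qualify by meeting the following criteria". The criteria that follow cover pregnancy, remaining in hospital, WBC and ferritin. ECMO is not among them. Section 5.2 sets daily SQ dosing for a week and does not mention ECMO.

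**The concern.** An entry exclusion need not be a stopping rule, and continuing the drug on ECMO may well be intended in the IV arms. The difficulty is narrower. One of the two ECMO exclusions rests on the SQ route, two of the four possible arms are SQ, and the section that governs exclusions arising later tells sites to carry on without distinguishing routes.

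What is at stake is the safety of the dosing instruction, not the trial's inference. A site in an SQ arm must either give injections that the protocol calls contraindicated or depart from a written rule. Section 10.4 counts the exclusion criteria among the protections against risk, and here one of them lapses after the first dose without explanation.

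**Working it through.** **Text comparison.** The question is whether any provision stops, holds or reroutes SQ dosing once ECMO has started.

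| Section | What it does about ECMO | Closes the gap? |
|---|---|---|
| 3.1 | Excludes at entry, once for SQ injection and once in general | No: applies at screening |
| 4.2.1 | Pauses immune screening until "the subject comes off CRRT or ECMO provided that the subject remains in the ICU" (among other conditions) | No: screening only, not dosing |
| 4.3 | Bars the first dose | No: first dose only |
| 4.4 | Not mentioned | No |
| 4.5 | Not mentioned | No |
| 4.7 | Orders continuation, no route named | No: this is the source |
| 5.2 | Not mentioned; no move to IV | No |

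Two details in 4.4 and 4.7 bear on this. Section 4.4 knows how to write a hold: for a high WBC, "GM-CSF should be withheld on this study day". Its daily physician authorization is triggered only by an SAE attributed, or probably attributed, to GM-CSF, so an ECMO start judged unrelated does not trigger it. In 4.7, the bullet on new immunosuppressive therapy leaves GM-CSF to the clinical team; the ECMO bullet leaves no such choice.

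**Doses at issue per child.** Let *k* be the last dose given before ECMO starts and *d* the number of scheduled dose times that fall during ECMO. With 7 scheduled doses, SQ doses given on ECMO are at most min(7 − *k*, *d*):

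| *d* | *k*=1 | 2 | 3 | 4 | 5 | 6 |
|---|---|---|---|---|---|---|
| 0 | 0 | 0 | 0 | 0 | 0 | 0 |
| 1 | 1 | 1 | 1 | 1 | 1 | 1 |
| 2 | 2 | 2 | 2 | 2 | 2 | 1 |
| 3 | 3 | 3 | 3 | 3 | 2 | 1 |
| 6 | 6 | 5 | 4 | 3 | 2 | 1 |

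The maximum is 6. The count is lower if the child dies, or if doses are held for WBC or stopped for ferritin.

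**Children treated by the SQ route.** Section 3.2 expects that "half of the subjects receiving GM-CSF will be evaluable" and that about a third of those enrolled qualify for drug. This reproduces its ceiling: 30 / 0.5 = 60 treated, and 60 × 3 = 180 enrolled. The same 0.5 applied to the paths in section 4.5 gives:

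- No IV arm succeeds: 0. This is inferred, since 4.5 opens an SQ arm after an IV success and does not say what happens otherwise.
- One SQ arm runs to 10 evaluable: 10 / 0.5 = 20.
- 125 mcg SQ fails at its 3rd non-responder (after 3 to 10 evaluable) and 250 mcg SQ then runs to 10: (3 + 10) / 0.5 = 26 up to (10 + 10) / 0.5 = 40.

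These counts are the pool in which the event could occur. They are not the number of children affected, which cannot be estimated without an ECMO rate.

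**The case against.** The strongest reply is that section 4.7 is deliberate. It sorts new exclusions into those that stop the drug (ferritin, pregnancy), one left to clinicians (immunosuppression) and one that continues it (CRRT or ECMO). On this view the authors considered ECMO and chose to continue; the text names no route, and nothing forces an intensivist to give an injection thought unsafe. Missed doses are foreseen and lead only to replacement. Stopping the drug is not withdrawal. A deterioration leading to ECMO would probably be reported as an SAE within 24 hours and seen by the medical monitor. The contraindication itself rests on one word in parentheses, with no mechanism given.

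Part of this stands. Harm is not shown, the event should be uncommon, and the primary decision is untouched. Giving the remaining doses IV is also a possible answer that the documents cannot rule out.

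The rest does not remove the conflict. The general safeguards do not countermand a specific instruction to continue. Deliberate continuation would explain the IV arms, but the only rationale offered is PK/PD, and CRRT and ECMO share one rule even though section 3.1 ties only ECMO to SQ injection. The natural reading of 4.7 with 5.2 in an SQ arm is a further SQ injection. The Manual of Operations is not available, but the ECMO bullet does not refer to it, while the immunosuppression bullet does.

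**Conclusion.** The concern holds and should be fixed. The protocol's rule, taken literally in an SQ arm, calls for injections by a route its own eligibility criteria describe as contraindicated, and no other section prevents this. The exposure is bounded at 6 doses per affected child and may be 0. The number of affected children is unknown and probably small, given the ECMO screens in 3.1 and 4.3.

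Confidence is high on the textual conflict. No claim is made about the size of harm, because the documents do not say why ECMO contraindicates SQ injection or whether the contraindication is absolute. The 8-of-10 rule, the evaluable count and the sample size are unaffected. The treated-child counts rest on the plan's own assumption that half of treated subjects are evaluable.

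**What to change.** Restrict the ECMO continuation rule in section 4.7 to the IV arms. Add one sentence to each of sections 4.4, 4.7 and 5.2: in the SQ arms GM-CSF is not given while the child is on ECMO. State there whether the remaining doses, up to Drug Day 7, may resume once ECMO ends. Section 4.2.1 already offers a pause-and-resume pattern. If the sponsor would rather give these doses IV, or continue SQ, the protocol should say so and give the reason.

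Replace the child as now planned; the drug-interruption bullet in 4.7 leads to the same result. Keep adverse event follow-up to Drug Day 21, or to discharge if that comes first, as section 4.10 provides.

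The cost is three sentences and a memo to sites, with no change to the success rule or sample size. The real loss is some PK and immune data, and possible treatment benefit, in the few SQ-arm children who start ECMO after their first dose.

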## 4.8 GM-CSF Pharmacokinetics

Pharmacokinetic (PK) data will be collected from subjects who receive study drug to evaluate drug clearance, volume of drug distribution, and therapeutically beneficial concentrations. The half-life of GM-CSF is sufficiently short (2-5 hours) that steady state pharmacokinetics (PK) are never reached. We will obtain GM-CSF levels from serum of enrolled subjects around the 3rd and 7th scheduled doses of drug. For these evaluations, 6-8 timed blood samples of 1 mL each for determination of serum GM-CSF concentration will be obtained from an existing intravenous or intra-arterial line at pre-specific time points around those doses. PK samples will only be collected if subjects have an indwelling vascular catheter that permits painless blood draws.

## 4.9 Other Sampling and Shipping

The remaining plasma from blood samples obtained for immune function monitoring (approximately 1.3 ml blood per sample) and post-drug samples will be collected, aliquoted, and stored for later analyses of the relationships between biomarkers of coagulation (e.g.,

PAI-1, thrombomodulin, angiopoietin-2) and immune function over time. Plasma will also be analyzed for levels of the cytokines IL-6 and IL-8 in order to assess the relationships between GM-CSF therapy and systemic inflammation over time. Endotracheal aspirates will be collected on immune function screening days and on each of the 7 days of GM-CSF dosing for analyses of the relationships between immune function and the airway microbiome in the setting of immunomodulatory drug therapy.

Screening samples and Drug Day 4 samples will be overnight shipped to the ISL as noted in Section 4.2. All other samples will be stored at the site and batch-shipped upon completion of each subject's participation in the GRACE study.

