Subjects who receive GM-CSF will undergo repeat innate immune function and ferritin testing the morning after their 3rd and 7th scheduled doses of GM-CSF to monitor the effect of GM-CSF on immunoparalysis associated with pediatric sepsis-induced MODS, as well as to reassess serum ferritin. Immune function testing is summarized in Figure 2.

[figure not shown]

Figure 2: Schematic of the GRACE Study

If the serum ferritin is  $\geq 2,000$  ng/ml, the subject ends further study participation permanently, and the site will be immediately notified so that site-specific confirmation and management of hyperferritinemia can take place.

The Nationwide Children's site is able to assess subject eligibility on the same day as LPS stimulation (MODS Day 2), but GM-CSF administration will be delayed until the next morning (MODS Day 3) in order to remain consistent with the dosing schedule at other CPCCRN sites.

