### 5 GM-CSF Administration

#### 5.1 IV Infusion Arms

The first dose of the study drug will be infused over a minimum of 6 hours on the day after the qualifying immune testing sample. The infusion may be interrupted if needed, but must run over a total of no more than 12 hours. GM-CSF may be given via a peripheral or central IV catheter. The first administered dose of GM-CSF will be initiated within 4 hours after receipt of notification of qualification for drug. If the 4 hours elapse, GM-CSF

	Schedule of Events	Drug Study Day										9-21/ hospital discharge	22 - hospital discharge
		1	2	3	4	5	6	7	8				
	GM-CSF administration	X	X	X	X	X	X	X					
	AE monitoring	X	X	X	X	X	X	X	X		X		
	AE resolution monitoring	X	X	X	X	X	X	X	X		X		X
	PK sampling			X				X					
	1.5 mL blood sample prior to GM-CSF (4AM- noon) immune function/ferritin testing				X				X				
	Sample shipment to Nationwide Initial immune function/ferritin testing				X								
	Tracheal aspirates	X	X	X	X	X	X	X	X				
	Batch shipment to Nationwide PK samples, tracheal aspirates, and final immune function samples	X	X	X	X	X	X	X	X				

Table 2: Summary of Study Events

should still be started as soon as possible. Subjects who have initiated the study drug treatment course will need to continually qualify for subsequent doses as indicated under the protocol section 4.4 for subsequent GM-CSF doses. All subsequent IV doses will be initiated between 4 AM and noon. If the window is missed, GM-CSF should still be given as soon as possible.

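### Drug Day 8 ferritin and immune function results come back only after an undefined end of participation, which delays the ferritin notice in 4.2 and the 125 mcg arm stop in 4.5

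*Combined protocol and SAP*

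**What the plan says.** - **Testing days (4.2).** "Subjects who receive GM-CSF will undergo repeat innate immune function and ferritin testing the morning after their 3rd and 7th scheduled doses of GM-CSF". The stated purposes include rechecking ferritin.
- **Ferritin consequence (4.2).** At 2,000 ng/ml or more, "the subject ends further study participation permanently, and the site will be immediately notified". The sentence names no sample day and follows the paragraph on both post-dose tests.
- **Shipping (4.9).** "Screening samples and Drug Day 4 samples will be overnight shipped to the ISL as noted in Section 4.2". Then: "All other samples will be stored at the site and batch-shipped upon completion of each" subject's participation. The batch-shipment row of Table 2 lists "PK samples, tracheal aspirates, and final immune function samples", which confirms that Day 8 goes by batch.
- **Arm rule (4.5).** A subject fails if the TNFα response is below 200 pg/ml on Drug Day 4 or Drug Day 8. "If a 3rd subject in a 125 mcg dose arm fails to respond to study drug, that arm is considered to have failed", and enrollment in that arm ends. The 250 mcg arms have no such stop.
- **Not stated.** The plan does not say when participation is complete, when a Day 8 result is due, or whether new starts in an arm wait for pending Day 8 results.

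**The concern.** Two rules depend on a result that the shipping plan holds back.

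The first is the ferritin notice. The trial excludes children with ferritin of 2,000 ng/ml or more because section 2.4 treats the MAS-like phenotype as a potential contraindication to GM-CSF. Table 2 has the Day 4 sample drawn before that day's dose, so Day 8 is the only planned study ferritin that reflects doses 4 to 7. Under 4.9 it leaves the site only once participation is over. The result then cannot end participation, and the notice cannot be immediate in any useful sense. If completion means Drug Day 21 or discharge, the result also arrives after adverse event recording has closed (11.2.1), although 11.2.2 has clinically significant laboratory abnormalities recorded as adverse events.

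The second is the third-failure stop. When the deciding failure shows only on Day 8, children can keep starting drug in a 125 mcg arm that has already failed by its own rule, instead of in the 250 mcg arm that 4.5 opens next.

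**Working it through.** **1. The plan's own figures (3.2).** It needs 20 to 30 evaluable subjects, with one third of those enrolled qualifying for drug and half of those treated evaluable.

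- Treated: 20/0.5 = 40 to 30/0.5 = 60.
- Enrolled: 40/(1/3) = 120 to 60/(1/3) = 180. The upper figure reproduces the stated maximum of 180.
- Accrual: 8 hospitals × 8 to 10 eligible a year = 64 to 80 a year, so 180 takes 180/80 = 2.25 to 180/64 = 2.8 years, consistent with up to three years. Spreading 180 over the full three years gives 60 a year.
- Treated starts: 60/3 = 20 to 80/3 = 26.7 a year. The upper end assumes that every eligible patient enrolls.
- Time to ten evaluable subjects: 10/(20 × 0.5) = 1 year to 10/(26.7 × 0.5) = 0.75 year, or about 9 to 12 months per arm.

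**2. New starts while one decisive Day 8 result is pending.** Mean m = (treated starts per year) × lag/365. The Poisson chance of at least one is 1 − exp(−m). The documents give no lag, so each one below is an assumption.

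| Assumed route for Day 8 | Lag (days) | Mean at 20/year | Mean at 26.7/year | Chance of at least one |
|---|---|---|---|---|
| Overnight | 1 | 0.05 | 0.07 | 5–7% |
| Batch, completion = Day 8 | 3 | 0.16 | 0.22 | 15–20% |
| Batch, completion = Day 21, result Day 22 | 14 | 0.77 | 1.02 | 54–64% |
| Batch, a further week | 21 | 1.15 | 1.53 | 68–78% |

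For example, 20 × 14/365 = 0.77 and 1 − exp(−0.77) = 0.54.

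**3. Averaged over arms that fail.** Step 2 applies when the third failure to become known is a Day 8-only failure. It arises at most once per failed 125 mcg arm, not once per failing subject. A simulation (20,000 arms per scenario, Poisson starts, half of treated evaluable, half of failures assumed visible on Day 4 and known by Day 5) counted starts beyond those under overnight Day 8 shipping. True response probabilities were 0.5 and 0.7.

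- Day 8 result on Day 22: mean 0.29 to 0.44 extra treated children per failed arm, with a 22 to 30% chance of at least one.
- Day 8 result on Day 11: mean 0.05 to 0.07, with a 4 to 6% chance.

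**4. Effect on arm success.** Three failures among ten leave at most seven successes, so the stop only cuts short an arm that can no longer reach 8 of 10. P(at least 8 of 10) is 0.055, 0.383 and 0.678 at true response probabilities of 0.5, 0.7 and 0.8, whenever Day 8 results arrive.

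**5. Ferritin.** No arithmetic is needed. Section 4.2 describes tests after doses 3 and 7 and then an immediate notice with no day excluded. Sections 4.4 and 4.7 attach the study-sample drug stop and the replacement rule to the Day 4 (post-third-dose) sample only. Section 4.9 and Table 2 hold Day 8 until participation ends. For a high Day 8 ferritin, 4.2 as worded and 4.9 cannot both be followed under any lag.

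**The case against.** Batch shipping looks deliberate. Sections 4.2 and 4.9 and Table 2 all refer to batching of later immune function samples, and real-time assay is kept for samples that govern dosing. The operational ferritin rules in 4.4 and 4.7 concern Day 4, no dose follows Day 7, and the 4.2 sentence could mean notification as soon as a result exists. Clinical laboratories may find hyperferritinemia independently, and adverse events are followed in hospital to Drug Day 21. The lag may also be short: 4.10 separates sampling from adverse event follow-up, and the batch row in Table 2 is marked for Days 1 to 8 only, though those marks may denote collection days.

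Most of this stands, and it limits the point. It does not remove the conflict over Day 8 ferritin, nor does it supply a definition of completion or a due date for Day 8 results.

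Several stronger readings are tempting but not supported:

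- **That the arm stop cannot work.** Shipping is per subject, not at study end, and Day 4 failures are known promptly. Against 9 to 12 months per arm, a lag of days to weeks makes the stop late, not inoperative.
- **That a dosing safeguard is lost.** What is delayed is a notice after the last dose. The documents give no window from which to conclude that it comes too late to act on.
- **That children enrolled during the lag count as extra exposure.** Enrollment is for immune screening, and only about one third are expected to qualify for drug.
- **That different storage biases Day 8 against Day 4.** Stimulation, incubation and centrifugation are done on site before shipping (4.2), and nothing in the documents shows degradation in storage.

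**Conclusion.** The point holds in limited form. Following 4.9 delays a safety notice that 4.2 states is immediate, and can let a child start drug in a 125 mcg arm that has already failed. The ferritin conflict needs no assumption about lag. The exposure cost is small and uncertain: while a decisive Day 8 result is pending, about 0.16 to 0.22 starts if the lag is 3 days and 0.8 to 1.0 if it is 14 days, against 0.05 to 0.07 with overnight shipping. Averaged over failed arms, it is 0.29 to 0.44 children if results arrive on Day 22 and half of failures show on Day 4. These figures rest on 20 to 27 treated starts a year, derived from 3.2, and on assumed lags. On the pathways that 4.5 spells out, the 125 mcg SQ arm opens only after 125 mcg IV has succeeded, so at most one 125 mcg arm can fail. It deserves correction because the remedy is cheap, not because the trial's conclusion is at risk.

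**What to change.** - In 4.9 and Table 2, move the Drug Day 8 immune function/ferritin sample to the overnight shipment and next-morning assay already used for screening and Day 4. PK samples and tracheal aspirates can stay batch-shipped.
- In 4.5, state that the arm tally is updated on receipt of each Day 8 result.
- Define completion of participation in 4.9 for the samples that remain batched.
- Reconcile 4.2, 4.5, 4.9 and Table 2 on whether immediate ferritin notification covers Day 8. The clinical response to a high value stays with site protocols.

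Cost: about 40 to 60 extra overnight shipments and unbatched assays, one per treated subject. This is an upper figure, because some treated subjects will not reach Day 8. The sample is already drawn and the route and assay already exist, so no new procedure is needed.
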